We created a battery of health measures to be specific to the management of BPH. The clinician will determine, on a case-by-case basis, the assessment schedule based on medical need, but sample schedules are presented in Tables 2.1 and 2.2 (medical management Table 2.1; surgical management Table 2.2). If a clinical follow-up visit is not required as part of standard of care as determined by the patient's personal physician (i.e., at Week 12 and Week 24 for medically managed patients), the follow-up visits can be completed remotely by phone, web, or app. Using PROs is already part of the management guidelines for BPH; the overarching hypothesis of this project is that a brief (i.e., clinically feasible) set of questions can aid in the management of BPH and can improve upon the existing method of the AUA-SI. We recognize that the proposed battery of measures is much longer than the one-page AUA-SI, but a longer battery of questionnaires is necessary for research purposes to clarify which measures would need to be dropped versus retained for use in the real-world clinic. In addition, scores from the one-page LURN SI-10 can be extracted from the longer 29-item questionnaire. Data analyses (see Section 1.4) will also include the LURN SI-10 score for maximum clinical relevance. Patients undergoing surgery will have more frequent queries in the immediate postoperative period (Table 2.2), as many men report bothersome symptoms of frequency, urgency, pain, and/or incontinence in this timeframe; thus, this period in particular is a target for better characterization and management of symptoms. We have had success with collecting data every 2 weeks as part of other research, supporting feasibility. Routinely collected objective clinical data, including urinalysis, prostate-specific antigen, uroflowmetry, post-void residual, prostate size, intravesical prostatic protrusion, and cystoscopic findings will also be collected and analyzed in combination with PROs.

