For assessment of test-retest reliability, patients will receive the LURN SI-29 and AUA-SI questionnaires in two instances, 2 weeks apart. 60 patients will be needed for test-retest reliability; therefore, participants will be approached until 60 patients have completed 2 scorable questionnaires. Patients consented prior to their baseline clinic visit will complete the questionnaires 2 weeks (range 1-3 weeks) prior and then again at the visit, while patients who enroll at the baseline visit and have a scheduled diagnostic procedure at least 1 week but no longer than 3 weeks later (e.g., cystoscopy and/or prostate transrectal ultrasound), with no

STU00217126  
EH22-021

treatments or interventions planned in the interim, will complete questionnaires at the baseline clinic visit and again 2 weeks (range 1-3 weeks) later. In this latter group of patients, we expect the lowest variation in symptoms over time due to minimal change in circumstances. In order to effectively assess test-retest reliability, we will target 2 weeks between questionnaire administration but will allow a 1-3-week time interval between questionnaires. The questionnaires will be delivered in Epic MyChart but could also be completed on paper or over the telephone; research coordinators will contact participants to remind them of these questionnaires in order to minimize missing data. Mode of administration will be recorded.

Table 2.1 Study questionnaires, medical/non-surgical intervention (Schedule of assessments: baseline, inter-visit follow-up, and clinic assessments)									
	# Items	Week -2	Baseline (clinic)	Week 4	Week 8	Week 12 (clinic)	Week 16	Week 20	Week 24 (clinic)
LURN SI-29	28								
PROMIS-29 Profile	29								
AUA-SI	8								
Patient Global Impression of Improvement (PGI-I)	1								
National Cancer Institute Quick Food Scan	17								
3-Day Voiding Diary	9								
PROMIS-GI: Constipation	9								
PROMIS-GI: Diarrhea	6								
SHIM	5								
MSHQ-EjD	4								
STOP-BANG	8								
PRO Cognitive Function – Short Form 4a	4								
Patient Feedback Survey (optional)	6								

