Note: Study time points (e.g., Week 4, Week 8) are approximate – Participants will be given a time window of $\pm$ 2 weeks. The minimum time between assessments will be approximately 4 weeks. Time windows may be adjusted based on COVID-19 protocols (e.g., if a clinic visit is converted to telehealth).									

STU00217126  
EH22-021**Table 2.2 Study questionnaires, surgical/procedural intervention  
(Schedule of assessments: baseline, inter-visit follow-up, and clinic assessments)**

	# Items	Baseline (clinic)	Preop **	Week 1	Week 2	Week 4 (clinic)	Week 6	Week 8	Week 12 (clinic)	Week 24 (clinic)
LURN SI-29	28									
PROMIS-29 Profile	29									
AUA-SI	8									
Patient Global Impression of Improvement (PGI-I)	1									
National Cancer Institute Quick Food Scan	17									
3-Day Voiding Diary	9									
PROMIS-GI: Constipation	9									
PROMIS-GI: Diarrhea	6									
SHIM	5									
MSHQ-EjD	4									
STOP-BANG	8									
PRO Cognitive Function – Short Form 4a	4									
Patient Feedback Survey (optional)	6									
Note: Study time points (e.g., Week 4, Week 8) are approximate – Participants will be given a time window of $\pm$ 2 weeks. The minimum time between assessments will be approximately 4 weeks. Time windows may be adjusted based on COVID-19 protocols (e.g., if a clinic visit is converted to telehealth). ** If surgery is not immediately scheduled, complete questionnaires every 4 weeks until surgery is scheduled.										

To assess MIDs, we will administer the PGI-I as a measure of global change at each post-baseline time point. The PGI-I is a single-item questionnaire that asks respondents to rate their condition compared with prior to treatment on a 7-point scale from very much worse (1) to very much better (7). LURN SI-29 and SI-10 scores at 12 weeks post-baseline will be used to assess changes in scores since baseline.

In addition, participants will be offered the opportunity to complete a patient-response burden questionnaire (patient feedback survey) at the end of their study participation. This will provide a better understanding of how the participants perceived the PROs.

STU00217126  
EH22-021

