**Minimizing missing data: Alternate data collection strategies.** The primary mode of data collection will be patients completing surveys administered electronically via Epic MyChart. There may be some patients who are unable to complete their questionnaires electronically due to a low level of technological literacy or other information technology issues. In such cases, they will be offered the chance to complete the questionnaires via paper packets, which will be administered in the same order as the electronic questionnaires. We will use the 29-item version of the PROMIS Profile, version 2.1. If a patient in this study has difficulties with both electronic and paper questionnaires, a research coordinator will read the questionnaire to the participant, including response options, and record their responses for inclusion in the analyses.

**Interviews.** To maximize convenience for participants (patients and providers), interviews will be conducted via telephone or secure end-to-end encrypted virtual interview (e.g., Zoom) by a trained interviewer. Participants' email addresses and phone numbers will be shared with the interviewer. Providers will be recruited from across the United States through email invitations and consented verbally before the interview. These invitations will include detailed information about the study's purpose, procedures, and the voluntary nature of participation. A trained researcher will use a qualitative interview guide to ask questions regarding healthcare coordination gaps. Interviews will be audio-recorded and transcribed. Audio recordings of interviews will be transcribed using a HIPAA-compliant service, such as "TranscribeMe." These recordings will not contain any identifiable information, ensuring participant confidentiality. The recordings will be securely transferred to the transcription service through an encrypted platform.

STU00217126  
EH22-021

Once the transcriptions are completed and securely returned, the transcription service will delete the audio recordings from their system. Transcriptions will be stored on a secure system (Box.com) accessible only to the research team, and all files will be reviewed to confirm the absence of any identifying details.

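### Test-retest pairs count toward the 60 without asking whether symptoms changed in between, and only one of the two recruitment routes rules out planned interim treatment

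*Protocol*

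**What the plan says.** All of this is in the protocol, section Procedures Involved, unless noted.

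- **Counting rule.** "participants will be approached until 60 patients have completed 2 scorable questionnaires". What is given twice is the LURN SI-29 and the AUA-SI, nothing else.
- **Interval.** "we will target 2 weeks between questionnaire administration but will allow a 1-3-week time interval between questionnaires".
- **First route.** "Patients consented prior to their baseline clinic visit will complete the questionnaires 2 weeks (range 1-3 weeks) prior and then again at the visit". No condition on treatment in the interval is attached.
- **Second route.** Men who enrol at the baseline visit, have a diagnostic procedure 1 to 3 weeks later and have no "treatments or interventions planned in the interim, will complete questionnaires at the baseline clinic visit and again 2 weeks (range 1-3 weeks) later". The protocol adds that it expects symptoms to vary least in this second group.
- **Change item.** The PGI-I is introduced for the MID work, is given after baseline, and "asks respondents to rate their condition compared with prior to treatment".
- **Mode.** "The questionnaires will be delivered in Epic MyChart but could also be completed on paper or over the telephone". The mode used is to be recorded. No rule asks for the same mode both times.
- **Who may enter.** Recruitment Methods admits new patients and patients returning under treatment.

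**The concern.** A test-retest coefficient measures the instrument only in people whose state has not moved. Here a pair qualifies by being scorable and on time; whether the man was stable is never established. The protocol recognises that stability matters, since it restricts interim treatment in one route and expects less variation there, but it lets both routes count equally toward the 60.

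A difference between two scores is then either measurement error or real change, and the data cannot tell which. Unrecognised change lowers the ICC and widens the spread of differences, so the LURN indices would look less precise than they are. Aim 2 hypothesises adequate reliability, so a large enough loss could alter that judgement. The item has to be in place before the pairs are collected, because an analysis plan can set changed men aside only if they were asked.

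**Working it through.** **Can the planned 60 be reproduced?** No. This document gives no target ICC, interval width, error rate or power for it. With assumed inputs, standard formulas land nearby: a 95% interval of width 0.20 needs 51 pairs at ICC 0.80 and 75 at ICC 0.75. The number 60 is plausible and is not disputed here.

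**Could the PGI-I identify stable men?** Take the routes in turn.
- First route: the retest is the baseline visit itself, and the PGI-I is given only after baseline.
- Second route: the retest comes after the baseline visit, but the PGI-I is not among the instruments listed for the pair. Its reference point is the time before treatment, not the first questionnaire. For a man not yet treated the question has no clear meaning; for a returning man under treatment it reaches back beyond the first questionnaire.

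The cells of Tables 2.1 and 2.2 are not readable in the text at hand, but this reasoning does not depend on them.

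**Effect of real change on the ICC (assumed inputs).** Scale the score to variance 1 at the first occasion, with person variance 0.85 and error variance 0.15. Let a share p of men change by D SD, equally often up and down. The covariance stays 0.85 and the second variance becomes 1 + pD², so

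ICC = 0.85 / (1 + pD²/2).

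| p | D = 0.5 SD | D = 1.0 SD |
|---|---|---|
| 10% | 0.85/1.0125 = 0.840 | 0.85/1.05 = 0.810 |
| 20% | 0.85/1.025 = 0.829 | 0.85/1.10 = 0.773 |
| 30% | 0.85/1.0375 = 0.819 | 0.85/1.15 = 0.739 |

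The variance of the differences rises from 0.30 to 0.30 + pD², so their SD grows by √(1 + pD²/0.30): √1.083 = 1.04 at the mild end and √2 = 1.41 at the extreme end.

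**Against sampling error.** An approximate 95% interval for an ICC of 0.85 from 60 pairs (Fisher z: atanh 0.85 = 1.256, plus or minus 1.96/√57 = 0.260) is 0.76 to 0.91. Only the cell with 30% and 1.0 SD falls outside it.

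**Effect of a mode shift (assumed inputs).** For a shift in one direction in a share p of pairs, the within-pair mean square is (1 − ρ) + E[D²]/2 and the between-pair mean square is 2(ρ + Var(D)/4 + (1 − ρ)/2). With ρ = 0.80, p = 30% and D = 0.3 SD, these are 0.2135 and 1.8095, giving an ICC of 1.5960/2.0230 = 0.789. Over shifts of 0.1 to 0.3 SD in 10 to 30% of pairs, the loss is about 0.01 at most.

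**Price of restricting to stable men.** The exact 95% interval at ICC 0.80 is 0.687 to 0.875 with 60 pairs, 0.665 to 0.885 with 45 and 0.624 to 0.899 with 30.

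**The case against.** **Stability is partly handled by design.** The interval is short and bounded, and the second route excludes planned treatment. That stands for that route as far as treatment is concerned. It does not detect spontaneous change, and the first route lacks even this condition.

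**The analysis plan may report by route or exclude unstable men.** Reporting by route is ordinary analysis-plan content, and the protocol does not say that a single pooled ICC is the only estimate. Excluding changed men is different, because no item records who they are. The AUA-SI is also given twice and could serve as a rough anchor, but it has its own measurement error and, as the Background says, leaves out incontinence and pain.

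**The bias is conservative and may be small.** True: it understates reliability and does not falsely validate the instruments. At the mild end it is 0.01. The smallest detectable change is not a named endpoint.

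**Stronger readings the document does not support.**
- A reader might infer that the telephone rule contradicts itself. Elsewhere "the follow-up visits can be completed remotely by phone, web, or app" applies to follow-up visits that usual care does not require. The fallback "If a patient in this study has difficulties with both electronic and paper questionnaires, a research coordinator will read the questionnaire to the participant" does not mention the telephone. These provisions and the test-retest mode list can all be followed together.
- A reader might infer that men drift to the telephone because staff ring them with reminders. The protocol says only that coordinators contact participants, and Recruitment Methods lists several channels.
- A reader might infer that mode effects must end up as unreliability. Mode is recorded, so the analysis can stratify or restrict, and the plausible effect on the ICC is small.

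**Conclusion.** The point holds in a limited form. Scorability and timing are the only completion conditions common to both routes. The condition on interim treatment covers one route only, and nothing described in the protocol separates real change from measurement error between test and retest.

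The size is unknown, because the protocol gives neither a rate of change nor an expected ICC. Under the assumptions of a true ICC of 0.85 and change of 0.5 to 1.0 SD in 10 to 30% of pairs, the expected ICC is 0.84 to 0.74. The extreme end, 1.0 SD in 30% of men within 1 to 3 weeks, is a strong assumption and the only case tabulated that exceeds the sampling error of 60 pairs. The change is worth making because it is cheap, concerns a named Aim 2 endpoint and cannot be made once the pairs are collected. It is not a threat to the study as a whole.

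**What to change.** 1. Add one item at the retest: *Since your last questionnaire, are your urinary symptoms better, about the same, or worse?*
2. Report reliability in men who answer *about the same*, beside the estimate for all pairs and for each route.
3. Apply the existing no-planned-treatment condition to both routes as a condition for entering the test-retest sample. This selects pairs and leaves care untouched.
4. Ask for the same mode both times where possible and use the recorded mode in a sensitivity analysis. Do not make it a counting rule or restrict the telephone: either would work against the protocol's aim of limiting missing data.

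**Cost.** One question at one time point, and a smaller stable subset. If 15 of 60 men report change, the interval at ICC 0.80 goes from about 0.69–0.88 to 0.67–0.89. If the team prefers 60 stable pairs and 10, 20 or 30% report change, it would need 60/0.9 = 67, 60/0.8 = 75 or 60/0.7 = 86 pairs (rounded up), from a cohort of up to 350.

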## RECRUITMENT METHODS

Patients—men with Benign Prostatic Hyperplasia (BPH) aged 50 years and older—will be recruited from Endeavor Health urology clinics as well as Swedish Hospital. This group has had much success in recruiting large samples of patients for research on LUTS. Both new and returning patients undergoing medical or surgical treatment for BPH will be eligible. Eligible patients will be identified in two ways: (1) A research coordinator will screen the electronic health record (EHR) for upcoming and past clinic appointments to identify patients who may be eligible. The coordinator will contact these patients by phone to describe the study and obtain informed consent remotely, which will be documented in Research Electronic Data Capture System (REDCap). Alternatively, (2) eligible patients who present for a clinic visit (either in-person or telehealth) will be referred to the coordinator to present the study, obtain informed consent (again either in-person or remotely), and document the consent and participant details in REDCap. During these interactions, research staff will explain the contents of the consent form focusing on the purpose of the study, study procedures, study duration, participants' rights and responsibilities, potential risks/benefits to participants, and how their protected health information will be used. Participants will be given the opportunity to ask questions about the study and will be provided with as much time needed to review and reach a voluntary decision on study participation.

For the 24-week duration of the study, participants will be contacted for study purposes by the research team via email, telephone, postal mail, secure end-to-end encryption, and Epic MyChart. The preferred method of communication for participants will be recorded.

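### The no-interim-treatment condition covers only one of the two test-retest routes, so pairs spanning a treatment change can count toward the 60 and lower the reliability estimate

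*Protocol*

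**What the plan says.** The protocol, PROCEDURES INVOLVED, sets the size and the counting rule: "60 patients will be needed for test-retest reliability; therefore, participants will be approached until 60 patients have completed 2 scorable questionnaires". Two routes supply the pairs.

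- **Pre-visit route.** "Patients consented prior to their baseline clinic visit will complete the questionnaires 2 weeks (range 1-3 weeks) prior and then again at the visit". Nothing is said about treatment in that interval.
- **Baseline-visit route.** This is for "patients who enroll at the baseline visit and have a scheduled diagnostic procedure at least 1 week but no longer than 3 weeks later", and only where there are no "treatments or interventions planned in the interim".

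Of the second route the protocol adds: "In this latter group of patients, we expect the lowest variation in symptoms over time due to minimal change in circumstances".

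Four other places bear on who can enter by the pre-visit route:

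- RECRUITMENT METHODS: "Both new and returning patients undergoing medical or surgical treatment for BPH will be eligible". To find them, a coordinator "will screen the electronic health record (EHR) for upcoming and past clinic appointments" and may obtain consent by phone.
- STUDY TIMELINES: the 24 weeks run from baseline or from the start of treatment, whichever is later, so treatment may begin before baseline.
- PRIMARY STUDY: INCLUSION AND EXCLUSION CRITERIA: a physician diagnosis with treatment planned is required. Recent genitourinary surgery is excluded; a recent start or change of BPH medication is not.
- Table 2.1 (medical management) has a Week -2 column and Table 2.2 (surgical) has none, so the scheduled pre-visit pairs belong to the medical schedule.

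**The concern.** A test-retest coefficient measures the instrument only if the respondents have not changed between the two administrations. The protocol protects one route against a change in treatment and leaves the other open, then pools both under a rule that asks only for two scorable questionnaires. A man on the pre-visit route whose BPH treatment is started, stopped or changed between Week -2 and baseline would contribute real symptom change, and the coefficient would record it as error.

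Test-retest reliability of the LURN SI-29 subscales and the SI-10 is an Aim 2 endpoint (STUDY ENDPOINTS), and the Aim 2 hypothesis also refers to precision for detecting change (OBJECTIVES). A coefficient that is too low would undersell the instruments and inflate any standard error of measurement derived from it. Nothing described would flag an unstable pre-visit pair: the PGI-I is given only after baseline, and the retest set is the LURN SI-29 and AUA-SI.

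**Working it through.** **The plan's own figure.** The 60 cannot be reproduced, because the protocol gives no target or null ICC, interval width, alpha or power. It is compatible with ordinary assumptions. For example, the Walter-Eliasziw-Donner formula with two ratings, null ICC 0.70 against 0.85, one-sided 5% and 90% power gives 58. The 60 is not in dispute.

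**Inputs for the size of the effect (all assumed; the protocol states none of them).**
- True reliability R = 0.85, with score variance 1 at the first questionnaire.
- A share p of the 60 pairs spans a treatment change.
- The mean shift in those pairs is d, in SDs of the score: 0.5 or 0.8. The protocol's only treatment-effect figure is a within-subject d of at least 0.5, from the SGM sub-study hypothesis (follow-up at 12 weeks). It is used here only for scale.

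**Formula.** With every affected pair shifted by the same d, the difference between administrations gains a mean of p·d and a variance of p(1−p)d². The agreement coefficient is

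2R / [2 + p(1−p)d² + (p·d)²] = 2R / (2 + p·d²) = R / (1 + p·d²/2).

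| p (pairs of 60) | d | Calculation | Agreement ICC |
|---|---|---|---|
| 10% (6) | 0.5 | 0.85 / 1.0125 | 0.84 |
| 20% (12) | 0.5 | 0.85 / 1.025 | 0.83 |
| 40% (24) | 0.5 | 0.85 / 1.05 | 0.81 |
| 20% (12) | 0.8 | 0.85 / 1.064 | 0.80 |
| 40% (24) | 0.8 | 0.85 / 1.128 | 0.75 |

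**If response varies between men.** Let the change in affected pairs have mean 0.5 SD and SD 0.5, independent of baseline. The added variance is then V = p·0.25 + p(1−p)·0.25, and the coefficient is 1.7 / [2 + V + (0.5p)²].
- p = 10%: 1.7 / (2 + 0.0475 + 0.0025) = 0.83
- p = 25%: 1.7 / (2 + 0.1094 + 0.0156) = 0.80
- p = 50%: 1.7 / (2 + 0.1875 + 0.0625) = 0.76

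**If a correlation is used instead.** The mean shift itself drops out and the loss is smaller. At p = 40% and d = 0.5 with a uniform shift, 0.85 / √(1 + 0.4·0.6·0.25) = 0.85 / √1.06 = 0.83, against 0.81 for agreement.

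**Against sampling error.** At n = 60 an ICC of 0.85 has a 95% interval of about 0.76 to 0.91, so all the 0.5 SD uniform-shift results lie inside it. The loss is nevertheless a bias in one direction, and more pairs collected under the same rule would not remove it.

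**Effect on the standard error of measurement.** At fixed SD, a fall from 0.85 to 0.80 raises it by √0.20 / √0.15 = 1.15, about 15%.

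**No change.** With p = 0 or d = 0 and no spread in change, the coefficient stays at R.

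**The case against.** The asymmetry has an ordinary explanation. For men enrolled at the baseline visit, the interval follows a visit at which treatment could begin, so a condition is needed. For men consented earlier, the interval precedes that visit, and inclusion refers to planned treatment. A new patient whose treatment is decided at baseline would normally be untreated throughout the interval. That stands, and it confines the problem to returning patients and to men who start, stop or change treatment inside the window. How many there are is not stated; they may be few.

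Three stronger readings are tempting, and the documents support none of them.
- A reader might infer that any pre-visit pair from a man on treatment is spoiled. Stable ongoing treatment does not lower test-retest reliability; only change across the interval does.
- A reader might take the protocol's remark about the latter group as an admission that the first group is unstable. It is a comparison and says no more than that.
- A reader might conclude that the coefficient will be biased. That depends on a share and a shift that the protocol does not give; if the share is near zero, there is no bias.

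It is also fair to say that the statistical analysis plan, which is not at hand, might exclude unstable pairs or report by route. That helps only in part. The collection rule and the stop at 60 are fixed in the protocol, so exclusions made afterwards would leave fewer than the 60 that it says are needed.

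**Conclusion.** The point holds in a limited form. The protocol's counting rule admits pre-visit pairs in which BPH treatment was started, stopped or changed between the two questionnaires, and no other section closes that gap. The direction of any effect on an agreement coefficient is downward. The size cannot be derived from the protocol. With an assumed true reliability of 0.85 it runs from about 0.01 (0.5 SD shift, 10% of pairs) through 0.04 (0.5 SD, 40%) to about 0.10 (0.8 SD, 40%). The larger values need both a large shift within one to three weeks and many affected pairs, so the smaller ones deserve more weight. The gap is worth closing because the endpoint is a named Aim 2 result and the remedy is cheap while recruitment is open.

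**What to change.** Apply one condition to both routes in PROCEDURES INVOLVED: a pair counts toward the 60 only if no BPH treatment was started, stopped or changed between the two questionnaires. Check it in the chart review already planned under DATA MANAGEMENT AND CONFIDENTIALITY. That section lists current medications and the type and date of BPH surgery, but no dates on which a drug was started or changed, so one field may have to be added. Keep approaching men until 60 such pairs exist.

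As a sensitivity analysis, report reliability by route, and again without men whose treatment changed recently before the first questionnaire. This belongs in a sensitivity analysis and not in the counting rule, because the protocol sets no such look-back for either route.

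The cost is one sentence, a chart check and perhaps a few more men approached within the planned cohort of up to 350. Patient care does not change.

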Shortly after the participant is consented into the study, they will receive PROs for the baseline or pre-baseline visit. PROs will be collected in accordance to the study schedule set forth for surgical or medical management, or the SGM substudy.

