## COMPENSATION FOR PARTICIPATION IN RESEARCH ACTIVITIES

### ***At Endeavor Health:***

Participants will receive a sum of \$60 in compensation for their time and effort by the completion of the study. They will be compensated after each completed study interaction as follows:

	Visit 1 (Baseline)	Visit 4 (12 Weeks Post-Treatment)	Visit 7 (24 Weeks Post-Treatment)	
Medical Management	\$20	\$20	\$20	
	Visit 1 (Baseline)	Visit 5 (4 Weeks Post-Procedure)	Visit 8 (12 Weeks Post-Procedure)	Visit 9 (24 Weeks Post-Procedure)
Surgical Management	\$15	\$15	\$15	\$15

Participants will receive their payments in the form of gift cards at the end of each completed clinical visit. Participants who complete audio-recorded interviews will receive an additional \$40 after each interview (at baseline, post-treatment, and follow-up) for a sum of \$120 for three interviews. Providers will receive a compensation of \$100.

STU00217126  
EH22-021

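### The note under Table 2.2 sets a minimum of about 4 weeks between assessments, but the table itself schedules surgical patients at Weeks 1, 2, 4, 6 and 8

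*Protocol*

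**What the plan says.** All of this is in the protocol.

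- **Procedures Involved, Table 2.2 (surgical/procedural).** The columns are Baseline, Preop, and Weeks 1, 2, 4, 6, 8, 12 and 24.
- **Note under Table 2.2.** "Participants will be given a time window of $\pm$ 2 weeks", and then "The minimum time between assessments will be approximately 4 weeks". The only exception named is adjustment for COVID-19. A further footnote covers the wait before surgery, with questionnaires every 4 weeks until surgery is scheduled.
- **Note under Table 2.1 (medical/non-surgical).** It carries the same sentences about windows and minimum spacing.
- **Procedures Involved, text before the tables.** "Patients undergoing surgery will have more frequent queries in the immediate postoperative period (Table 2.2"), with the reason that this period is a target for better characterization and management of symptoms. On feasibility: "We have had success with collecting data every 2 weeks as part of other research, supporting feasibility". The same paragraph leaves the schedule to the clinician case by case and says that "sample schedules are presented in Tables 2.1 and 2.2".
- **Consent Process.** "PROs will be collected in accordance to the study schedule set forth for surgical or medical management".
- **Compensation, Endeavor Health table.** For surgical management, Week 4 is Visit 5, Week 12 is Visit 8 and Week 24 is Visit 9.

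**The concern.** The note fits the 4-weekly grid of Table 2.1 and appears to have been carried over to Table 2.2 without adaptation. There it forbids the dense early follow-up that the table sets out and the text says is intended.

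Site staff then have two ways to act, and neither is satisfactory. If they apply the minimum, early post-operative assessments are skipped and cannot be recovered later. If they follow the column headings, windows of ±2 weeks around visits 1 or 2 weeks apart do not show which visit an early form belongs to. Either way the loss falls on the period in which the protocol expects bothersome symptoms, and on the early part of the symptom trajectories that are the Aim 1 endpoint.

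**Working it through.** **Inputs.** Post-operative weeks 1, 2, 4, 6, 8, 12, 24 (Table 2.2); window ±2 weeks and minimum spacing 4 weeks (note under Table 2.2); up to 225 medical and 125 surgical participants (Procedures Involved). Day 0 is taken as the procedure date, since the Compensation table counts surgical visits in weeks post-procedure.

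**1. Gaps at nominal weeks.** 2−1 = 1, 4−2 = 2, 6−4 = 2, 8−6 = 2, 12−8 = 4, 24−12 = 12. Four of six are below 4 weeks.

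**2. How many visits satisfy the minimum at nominal weeks.** Among Weeks 1, 2, 4, 6 and 8, no three are pairwise at least 4 weeks apart, so the maximum is 2 of 5 (for example Weeks 4 and 8). Adding Weeks 12 and 24 gives 4 of 7.

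**3. The same with full use of the windows.** The Week 8 window closes at day 70. Forms spaced 28 days apart from day 0 fall on days 0, 28 and 56; the next would be day 84, which is too late. Starting at day −7 gives −7, 21 and 49, then 77, also too late. The maximum is 3 of 5 early visits, and with Weeks 12 and 24 it is 5 of 7. At least 5 − 3 = 2 early assessments are lost.

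**4. How far *approximately* would have to stretch.** Five early forms need four gaps between day 0 and day 70: 70/4 = 17.5 days = 2.5 weeks. If the first form could precede surgery (day −7), it is 77/4 = 19.25 days = 2.75 weeks. With forms from day 0:

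| Minimum read as | Early visits that fit |
|---|---|
| 4 weeks | 3 of 5 |
| 3.5 weeks | 3 of 5 |
| 3 weeks | 4 of 5 |
| 2.5 weeks | 5 of 5 |

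**5. Window overlap.** The windows in days are:

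| Visit | Window |
|---|---|
| Week 1 | −7 to 21 |
| Week 2 | 0 to 28 |
| Week 4 | 14 to 42 |
| Week 6 | 28 to 56 |
| Week 8 | 42 to 70 |

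Of the 57 days from 0 to 56, three windows hold on days 14–21 (8 days), 28 and 42, which makes 10 days. The other 57 − 10 = 47 days lie in two windows, and none lies in only one. Day 14 is in window for Weeks 1, 2 and 4. Read literally, Week 1 opens a week before surgery, although Preop has its own column.

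**6. Are the columns meant as separate visits?** Counting them in order gives Baseline 1, Preop 2, Week 1 = 3, Week 2 = 4, Week 4 = 5, Week 6 = 6, Week 8 = 7, Week 12 = 8, Week 24 = 9. This matches the Compensation table's 5, 8 and 9 only if every column counts. The PGI-I is also planned at each post-baseline time point.

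**7. Comparison with Table 2.1.** From baseline to Week 24 all six gaps are exactly 4 weeks, and neighbouring windows touch without overlapping. The Week −2 retest form is the exception, and it has its own 1–3-week rule in Procedures Involved.

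**The case against.** The conflict and the arithmetic are not in dispute; the argument on the other side is that little follows from them.

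- **Staff would ignore a leftover sentence.** The headings, the text and the visit numbering all point to dense early follow-up, so skipping is unlikely. This is fair as to probability, and the loss of assessments is therefore stated only as what happens if the note is applied. It is still a written rule that the schedule breaks.
- **The schedules are samples and the time points approximate.** This lowers the stakes and permits departures. It does not turn gaps of 1 or 2 weeks into 4; the sample itself fails its own note.
- **Assigning forms to visits belongs in the SAP, or the label may follow the form sent.** Either may be so; the SAP was not available for this check. Neither removes the contradiction in the protocol, and no analysis rule restores an assessment that was never requested.
- **Nobody would file a pre-surgery form as Week 1.** Agreed in practice. It is a minor sign that the window was not written for this table.
- **Visit numbers in the compensation tables are not reliable throughout.** The table for the SGM sub-study calls its 12-week survey Visit 4, although Table 2.3 has two assessments. The numbering is therefore supporting evidence only; the headings and the text carry the point.
- **125 is an enrolment cap, not a count of people harmed.** Correct, and it is used here only as an upper bound.

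**Conclusion.** The concern holds. Under its own note the post-operative schedule of Table 2.2 cannot be carried out on any reading of the minimum above 2.5 weeks with forms from day 0. Applied as written, the note leaves at most 3 of the 5 early assessments.

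The reach is limited. The change score at 12 weeks is little affected, because the Week 12 assessment can be kept under either reading. The test-retest pair has its own interval, and Table 2.1 follow-up can meet the note. What is exposed is the early surgical course in up to 125 participants. This should be fixed, but it does not threaten the study as a whole.

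The conclusion assumes that at least one questionnaire is due in each column. The cell marks of Table 2.2 could not be seen in the text available, but the headings, the PGI-I plan and the stated early frequency support it.

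**What to change.** Reconcile the note with Table 2.2 by giving that table its own note, limited to questionnaire timing:

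1. State that the 4-week minimum does not apply to post-operative questionnaires scheduled closer together. If the sponsor does intend the minimum to apply, the columns, the text on early frequency and the visit numbering must change instead.
2. Make the windows non-overlapping, with a rule for shared end days. One example cuts at the midpoints between neighbouring visits (days 10.5, 21, 35, 49 and 70) and counts a shared end day to the earlier visit: Week 1 = days 1–10, Week 2 = 11–21, Week 4 = 22–35, Week 6 = 36–49, Week 8 = 50–70.
3. Let no post-operative window open before the procedure date.
4. Record the actual completion date and place each form by days since the procedure.

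The cost is a footnote amendment and adjusted release dates for the electronic questionnaires. Some early forms will fall outside the narrower windows, but they remain usable at their actual date.
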